2.9 DISSEMINATION OF RESULTS

The members of the study's research team are committed to disseminating the results in scientific media, supports and publications.

2.10 EXPENSES AND FINANCIAL COMPENSATION

This study is exempt from financial compensation to participants.

ANNEX I

INCLUSION CRITERIA FOR THE FORMATION OF THE "MICHIGAN SPLINTS" GROUP

- Be of legal age
- To be able to attend Polyclinic for 6 months
- Require a Michigan type acrylic relaxation splint.
- Not pregnant
- Not be breastfeeding

EXCLUSION CRITERIA:

- Being a minor
- Allergy to any type of plastic material, acrylic or resins used in dentistry.

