increase from 6% in 2019, to 23% at present, in Spain ((Carrillo-Diaz et al., 2022; Dias et al., 2022; *List of Results: BRUXISM INCREASE AFTER COVID: EBSCOhost*, n.d.; Osses-Anguita et al., 2023). This is because its aetiology is closely associated with stress. One of the consequences of bruxism is the fracture of teeth, whether or not they are devitalised. As an alternative, the restoration of lost tooth tissue is indicated with inlays made of ceromers (among others). These materials fall into the group of dental composites (divided into reinforced, universal, flowable and other composites for everyday clinical use), whose global market was valued at US\$ 24.7 Mn in 2021. It is estimated to grow at a CAGR of 9.0% from 2021 to 2031, and by the end of 2031, the global dental composites market is expected to reach a value of US\$ 59.3 Mn. This trend extends to all fields of dentistry, due to its characteristics, as described above. The dental materials industry is also focusing on improvements in the manufacturing process of the devices (injection moulded, subtraction or milled, addition or horizontal/vertical impression) achieving a sustainable, environmentally friendly, economical practice, and releasing fewer additives (Alhazzawi, 2016; Aretxabaleta et al, 2021; Carneiro Pereira et al., 2021; de Oliveira Limírio et al., 2021; Mourouzis et al., 2020, 2022; Wei et al., 2022). In particular, 3D printing is more environmentally friendly than milling because it does not use discs, which are more costly and complex to reuse.

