The main problem when studying the presence of additives released by dental materials in the organism is the extraordinary difficulty in associating them explicitly to this type of device, given that they are commonly found in our surroundings. Their multiple origins: environmental, nutritional, hygienic sources, etc., make it extremely difficult to associate the origin with the substance identified. For this reason, in vitro studies are a widely used method. However, the protocols developed to date show a certain lack of uniformity: in some, discs are analysed without considering the inhibited layer, in others their polishing does not correspond to the clinical protocol, or there is a lack of uniform extraction ratio, or the solvents are different, or salivary turnover is not taken into account (the possible alterations in its composition, pH, viscosity, or flow that may occur in the same subject, and its role in the chemical erosion of the material). On the other hand, in some of these tests, occlusal wear is not considered. They provide data on quantification and identification of the substances in saliva, mainly bisphenols, substitutes for

and phthalates, in different materials, depending on their manufacturing technique (milled, printed, injected), and their curing (thermo-, self-, photopolymerised). Clinical studies focus on paired samples, or on epidemiological, retrospective descriptive, comparative, retrospective and prospective studies where saliva, blood and urine samples are analysed to determine their assimilation. Among the methodologies used, the FDA (Food and Drug Administration) recommends High Performance Liquid Chromatography (HPLC) or Gas Chromatography (GC). Authors such as Hampe Tristan, advise Mass Spectrometry (MS), or the HPLC/MS tandem, establishing as ideal the combination of High Resolution Mass Spectrometry (HRMS) and MS, since it does not detect products such as Bis GMA, -EMA and -UDMA (De Angelis et al., 2022; Hampe et al., 2022; Kessler et al., 2020; Tichy et al., 2021). (Francisco et al., 2022; Van Landuyt et al., 2011a, 2011b; Vervliet et al., 2022; Wedekind et al., 2021).

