1.3 JUSTIFICATION

This study is framed within the European Community framework on substances that can have an impact on the health and well-being of the population, focusing on their identification, quantification, monitoring and prevention. The population susceptible to treatment of this kind is almost universal. Companies are investing in improvements in this respect, incorporating substitutes to bisphenols, with effects yet to be confirmed, generating a very dynamic and growing market. The literature demands more solid results and improvements in protocols. The Supramolecular Analytical Chemistry (SAC) research group at the University of Cordoba has developed an innovative, sustainable, specific and more economical method based on the use of supramolecular solvents (SUPRAS) combined with high performance liquid chromatography-high performance mass spectrometry (HPLC-HRMS/MS). This method allows the identification of compounds (known and unknown) by covering a wider range of substances present in the materials under study than solvents.

organic waste cannot be dealt with. Given that this method has not yet been implemented in dentistry, despite being amply tested, this pilot study has been developed to lay the foundations of a protocol, and to have a more exact and extensive knowledge of our treatments. One of the most widely used, especially after the pandemic, is the Michigan type acrylic splint, as a treatment for bruxism. It is also a removable device, which is used at least 6-8 hours a day, and does not involve the use of additional plastic materials that could be other sources of additives, such as cements, sealants or dental temporaries, as is the case with fixed prostheses. The population eligible for such treatment must have completed their bone and tooth growth (18 years of age or older). In the present study, two forms of manufacture were chosen: conventional and printed. The reason for not choosing the milled ones is because the latter generate more waste, and their mechanical response as well as the patient's preference are not better. Therefore, identifying the substances released by the acrylics, using SUPRAS and HPLC-HRMS/MS, by contrasting the *in vitro* and *in vivo* results, may shed some light on this issue.

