2.6 DESCRIPTION OF THE STUDY

2.6.1 VOLUNTEER RECRUITMENT:

The study groups will be formed in accordance with the requirements and inclusion criteria. Each of the subjects will be informed of the purpose and methodology of the project by means of an information document for the volunteer (Appendix II) and must sign the informed consent form provided for this purpose (Appendix III); they may withdraw from participation at any time. The data of the participants will be stored in a clinical history with an individual key number, in accordance with the regulations contained in the current Organic Law 3/2018, of 5 December, on the Protection of Personal Data.

Appointments will be made as follows:

APPOINTMENT 1: A conventional computerised clinical history is taken of the patient, in which data is collected on general health, orofacial and nutritional habits and hygiene. We explain in detail what the treatment consists of: Michigan type relaxation splint (device to prevent tooth wear due to bruxism). Each intervention is governed by scientific and deontological criteria, respecting all the ethical rules of research. The following is a detailed description of the study, its duration and methodology. The four moments of saliva collection will be explained: before, during, and 3 and 6 months after placement, as follows:

-Time 0: the day of the appointment, before the intervention.

-Step 1: On the day of the appointment, device placement.

-Time 2: 3 months after device placement.

-Time 3: 6 months after treatment.

Information and informed consent will be provided.

APPOINTMENT 2: Preparation and taking of models for the Michigan type splint according to the conventional protocol for this treatment.

APPOINTMENT 3: The models will be assembled in the articulator to send and request the making of the splint, specifying whether it is injected or printed.

APPOINTMENT 4: A saliva sample is taken in the device for this purpose. After checking for proper fit and retention, the occlusal adjustments will be made with a handpiece and conventional acrylic and polishing burs. After completion of the procedure, a new saliva sample shall be taken. The samples shall be identified with the patient's assigned code and stored according to conventional standards. An appointment will be made after 6 months to continue with the study and in accordance with the check-up times for correct oral health.

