Thus, knowing the possible elements identified, the saliva samples can be treated. This is carried out with a volatile supramolecular solvent spontaneously synthesised by adding hexanol and tetrahydrofuran. The methodology to be followed is the same as previously described in the *in vitro* phase.

Dependent variables: substances of very high concern and endocrine disruptors. Independent variables: usual residence, type of manufacture (printed or injected), time, age, type of polymerisation.

After identification and quantification of the detected substances, the data will be collected in a database with the volunteer's information (ANNEX IV).

Finally, the results will be analysed and correlated with those obtained in the experimental laboratory phase, and the possible participating variables: age, type of material, type of manufacture and habits of the participant (figure 2).

[figure not shown]

Figure 2. Timeline of *in vivo* pilot study on substances released from injected or printed acrylic occlusal splints. University Polyclinic of the European University of Madrid.

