ANNEX IV

Voluntary code	CONCENTRATIONS	CONCENTRATIONS	CONCENTRATIONS	CONCENTRATIONS
	M. Saliva 0	M. Saliva 1	M. Saliva 2	M. Saliva 3
SUBSTANCES				

 Name, surname, ID number and signature of the researcher _____
Date

Sample collection table for each volunteer

VARIABLES	Volunteer 1	Volunteer 2	Volunteer 3	Volunteer 4	Volunteer 5
AGE	-				
GENDER (MALE, FEMALE, OTHER)					
MATERIAL (ACRYLIC)					
MANUFACTURING (INJECTED or PRINTED)		-			
USUAL RESIDENCE (URBAN, RURAL)			-		
EXPOSURE TIME (HOURS) BRUXIST (YES/NO)				-	
REFLUX (YES/NO)					
ANTIDEPRESSANTS (YES/NO)					
ANTIHISTAMINES (YES/NO)					
DECONGESTANTS (YES/NO)					

BIBLIOGRAPHY

- Alhazzawi, T. F. (2016). Advancements in CAD/CAM technology: Options for practical implementation. *Journal of Prosthodontic Research*, *60*(2), 72-84.
<https://doi.org/10.1016/J.JPOR.2016.01.003>
- Alharbi, H. F., Algonaiman, R., Alduwayghiri, R., Aljutaily, T., Algheshairy, R. M., Almutairi, A. S., Alharbi, R. M., Alfurayh, L. A., Alshahwan, A. A., Alsadun, A. F., & Barakat, H. (2022). Exposure to Bisphenol A Substitutes, Bisphenol S and Bisphenol F, and Its Association with Developing Obesity and Diabetes Mellitus: A Narrative Review. *International Journal of Environmental Research and Public Health*, *19*(23).
<https://doi.org/10.3390/ijerph192315918>
<https://doi.org/10.1016/J.ADDMA.2020.101693>
- Bisphenol A and incisor molar hypomineralisation:: A review - Dialnet* (n.d.). Retrieved June 17, 2023, from <https://dialnet.unirioja.es/servlet/articulo?codigo=7998248>
- Carneiro Pereira, A. L., Bezerra de Medeiros, A. K., de Sousa Santos, K., Oliveira de Almeida, É., Seabra Barbosa, G. A., & da Fonte Porto Carreiro, A. (2021). Accuracy of CAD-CAM systems for removable partial denture framework fabrication: A systematic review. *Journal of Prosthetic Dentistry*, *125*(2), 241-248.
<https://doi.org/10.1016/j.prosdent.2020.01.003>

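### Resin or acrylic added to the mouth after the baseline saliva sample is neither excluded nor recorded, so the 3- and 6-month samples cannot separate it from the splint

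*Protocol*

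**What the plan says.** **Eligibility.** Annex I of the protocol lists two exclusions: being a minor, and "Allergy to any type of plastic material, acrylic or resins used in dentistry". The inclusion criterion on the device is "Require a Michigan type acrylic relaxation splint". No criterion concerns other resin or acrylic in the mouth, at entry or later.

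**Data collected.** The per-sample table in Annex IV holds substance concentrations for saliva samples 0 to 3 and nothing else. The second table has one entry per volunteer: age, gender, splint material, manufacture, residence, hours of exposure, bruxism, reflux and three drug classes. Section 2.6 gives the analysis variables as "Independent variables: usual residence, type of manufacture (printed or injected), time, age, type of polymerisation". At the first appointment, "data is collected on general health, orofacial and nutritional habits and hygiene". The later check-ups look at oral health and the state of the splint. None of these places names restorations, other devices or dental work between visits.

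**Control.** Section 2.1 makes each volunteer his or her own control through paired samples.

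**Attribution.** Section 1.2 treats linking a substance to a dental device as the central difficulty of such research, because the many possible sources "make it extremely difficult to associate the origin with the substance identified". Section 1.3 prefers the splint partly because it "does not involve the use of additional plastic materials that could be other sources of additives", and gives cements, sealants and temporaries as examples of such sources.

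**The concern.** The protocol recognises that other dental plastics release additives, and chooses a device whose fitting brings none of them. It then follows volunteers for months without recording whether such a source has entered the mouth in the meantime.

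A within-subject comparison is sound only for what stays the same between the two samples. If a volunteer has a filling, a cemented inlay, a temporary or another acrylic device placed or repaired after Time 0, a rise in a shared substance at Time 2 or Time 3 has two possible explanations, and the data as specified cannot tell them apart. No group goes without a splint, so background change would not show up that way either. The error would favour finding release from the splint. It could also distort the comparison of printed with injected splints if such work fell unevenly between groups of 15.

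The setting makes this plausible. Volunteers come from a dental polyclinic's database (section 2.4). Section 1.2 names tooth fracture as a consequence of bruxism, for which "the restoration of lost tooth tissue is indicated with inlays made of ceromers".

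**Working it through.** The point rests mainly on reading the document. The arithmetic only shows how many volunteers might be involved.

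**Step 1. Which samples are exposed?**
- Time 0 and Time 1 are both taken at appointment 4 (section 2.6), before and after the splint is adjusted. No outside dental work can fall between them.
- Time 2 and Time 3 are listed at 3 and 6 months. Work done in those intervals falls between Time 0 and the later sample.

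**Step 2. Which sources cancel?** Write a volunteer's salivary level at time t as B + S(t) + R(t), where B is the constant background (including stable restorations and devices), S is release from the splint and R is release from resin added after Time 0. At Time 0, S and R are both zero. The paired difference is then

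(B + S(t) + R(t)) − B = S(t) + R(t).

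B drops out and R(t) does not. The plan can read the difference as S(t) only if R(t) is zero or known. Annex I does not make it zero and Annex IV does not make it known.

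**Step 3. Which substances can be confused?** Sections 2.6 and 2.6.1 first identify what the splint material releases in vitro, and the saliva work is guided by that list. R(t) therefore matters only for substances that are on the list and also come from the added material. Section 1.1 names monomers for dental polymers, acrylics and composites as one family, from cements and sealants to splints. Overlap is plausible, but the protocol does not show it for these particular splint materials.

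**Step 4. How many volunteers?** Inputs:
- From section 2.4: 15 per group, 15 + 15 = 30 in total. This is a pilot size with no effect size, standard deviation or power, so there is no calculation to reproduce.
- Assumed, because the protocol gives no figure: a probability p of 5%, 10% or 20% that a volunteer has new resin work before the last sample.

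Expected number affected = n × p. Chance of at least one = 1 − (1 − p)^n.

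| Assumed p | Expected among 30 | At least one among 30 | At least one in a group of 15 |
|---|---|---|---|
| 5% | 30 × 0.05 = 1.5 | 1 − 0.95^30 = 79% | 1 − 0.95^15 = 54% |
| 10% | 30 × 0.10 = 3 | 1 − 0.90^30 = 96% | 1 − 0.90^15 = 79% |
| 20% | 30 × 0.20 = 6 | 1 − 0.80^30 = 99.9% | 1 − 0.80^15 = 97% |

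These are counts of people, not sizes of bias. The protocol gives no concentrations from which the effect of one affected volunteer on a mean or median could be worked out.

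**The case against.** Several objections have force.

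- **The preference for the splint is about the procedure.** Section 1.3 compares fitting a splint with fitting a fixed prosthesis. It does not claim that the rest of the mouth is free of resin. This is right: Annex I does not break a stated premise. The passage still shows that the protocol regards cements, sealants and temporaries as competing sources.
- **Pairing already deals with existing restorations and devices.** It does so where they are stable. That limits the point to what is added or repaired after Time 0.
- **The in vitro list filters the rest.** It does so in part. A substance that is not on the splint's list cannot be misattributed, but a shared one can.
- **The clinic would know.** A clinical history is taken and the mouth is examined at both later visits, so work done at the polyclinic may well be in its records. Nothing, however, carries that information into the study database, and work done elsewhere might not be noted.
- **It belongs in a statistical analysis plan.** The handling of affected samples could. The data field could not, because no analysis can use what was never collected.

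A reader might also infer something stronger: that new resin work is to be expected in these patients, and that it alone could produce a significant result. Six volunteers turning from not detected to detected, with none the other way, give an exact McNemar p of 2 × 0.5^6 = 0.031. With assumed rates of 10%, 20% and 30%, the chance of at least six among 30 is 7%, 57% and 92%. The documents do not support this reading. Section 1.2 gives no rate, and section 2.7.5 counts avoiding further dental damage among the splint's benefits. Section 2.8 names no paired test. The percentages also require every affected volunteer to be undetected at Time 0 and detected later, although section 1.2 says these substances are common in the surroundings. If half of those affected converted, the chances fall to 0.3%, 7% and 29%. The scenario is an upper bound and should be read only as that.

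**Conclusion.** The point holds in a limited form. As written, the protocol cannot distinguish release from the splint from release by resin, cement, sealant, temporary or acrylic devices added after Time 0. This applies to Time 2 and Time 3, and to substances that the added material shares with the splint's in vitro list. The Time 0 to Time 1 contrast and stable existing restorations or devices are not the problem.

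The size is uncertain because no rate is given. At an assumed 5% to 20% per volunteer, between 1.5 and 6 of the 30 would be affected, and at least one almost certainly would be at the upper end (79% at the lower end). Whether that shifts the results materially depends on the overlap of substances and on how much the added material releases, neither of which the protocol states. It would be wrong to say that such work will be counted as splint release; it could be, and nobody could check afterwards. For a pilot meant to lay the foundations of a protocol, that is worth correcting.

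**What to change.** **Annex IV, Time 0:** add a field for existing resin restorations and for any other acrylic device in use. This gives the reference against which later change is judged.

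**Annex IV, Times 2 and 3:** add a field for any resin, cement, sealant, temporary or acrylic device placed or repaired since the last sample, with the date.

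**Section 2.8:** add a sensitivity analysis of the Time 0 versus Time 2 and Time 0 versus Time 3 contrasts that leaves out samples taken after such work, and report the number left out in each manufacturing group.

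**Cost:** a few extra fields, filled by asking the volunteer and checking the clinic's record at visits that already take place, and one further analysis with slightly fewer late samples. Eligibility, recruitment and dental care stay as they are. If sampling is already complete, the fields would have to be rebuilt from clinic records, which may miss work done elsewhere; the report should then state this limitation.

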ANNEX IV

Voluntary code	CONCENTRATIONS	CONCENTRATIONS	CONCENTRATIONS	CONCENTRATIONS
	M. Saliva 0	M. Saliva 1	M. Saliva 2	M. Saliva 3
SUBSTANCES				

 Name, surname, ID number and signature of the researcher _____
Date

Sample collection table for each volunteer

VARIABLES	Volunteer 1	Volunteer 2	Volunteer 3	Volunteer 4	Volunteer 5
AGE	-				
GENDER (MALE, FEMALE, OTHER)					
MATERIAL (ACRYLIC)					
MANUFACTURING (INJECTED or PRINTED)		-			
USUAL RESIDENCE (URBAN, RURAL)			-		
EXPOSURE TIME (HOURS) BRUXIST (YES/NO)				-	
REFLUX (YES/NO)					
ANTIDEPRESSANTS (YES/NO)					
ANTIHISTAMINES (YES/NO)					
DECONGESTANTS (YES/NO)					

BIBLIOGRAPHY

- Alhazzawi, T. F. (2016). Advancements in CAD/CAM technology: Options for practical implementation. *Journal of Prosthodontic Research*, *60*(2), 72-84.
<https://doi.org/10.1016/J.JPOR.2016.01.003>
- Alharbi, H. F., Algonaiman, R., Alduwayghiri, R., Aljutaily, T., Algheshairy, R. M., Almutairi, A. S., Alharbi, R. M., Alfurayh, L. A., Alshahwan, A. A., Alsadun, A. F., & Barakat, H. (2022). Exposure to Bisphenol A Substitutes, Bisphenol S and Bisphenol F, and Its Association with Developing Obesity and Diabetes Mellitus: A Narrative Review. *International Journal of Environmental Research and Public Health*, *19*(23).
<https://doi.org/10.3390/ijerph192315918>
<https://doi.org/10.1016/J.ADDMA.2020.101693>
- Bisphenol A and incisor molar hypomineralisation:: A review - Dialnet* (n.d.). Retrieved June 17, 2023, from <https://dialnet.unirioja.es/servlet/articulo?codigo=7998248>
- Carneiro Pereira, A. L., Bezerra de Medeiros, A. K., de Sousa Santos, K., Oliveira de Almeida, É., Seabra Barbosa, G. A., & da Fonte Porto Carreiro, A. (2021). Accuracy of CAD-CAM systems for removable partial denture framework fabrication: A systematic review. *Journal of Prosthetic Dentistry*, *125*(2), 241-248.
<https://doi.org/10.1016/j.prosdent.2020.01.003>
